### **8.1.1.2 Consent/Assent and Collection of Specimens for Future Biomedical Research**

The investigator or medically qualified designee will explain the FBR consent/assent to the participant, or the participant's legally acceptable representative, answer all of his/her questions, and obtain documented informed consent/assent before performing any procedure related to FBR. A copy of the informed consent/assent will be given to the participant before performing any procedure related to FBR.

### **8.1.2 Inclusion/Exclusion Criteria**

All inclusion and exclusion criteria will be reviewed by the investigator who is a qualified physician to ensure that the participant qualifies for the study.

### **8.1.3 Participant Identification Card**

All participants will be given a participant identification card identifying them as participants in a research study. The card will contain study site contact information (including direct telephone numbers) to be used in the event of an emergency. The investigator or qualified

designee will provide the participant with a participant identification card immediately after the participant provides documented informed consent/assent. At the time of intervention allocation/randomization, site personnel will add the treatment/randomization number to the participant identification card.

The participant identification card also contains contact information for the emergency unblinding call center so that a healthcare provider can obtain information about study intervention in emergency situations where the investigator is not available.

#### **8.1.4 Medical History**

A medical history will be obtained by the investigator or qualified designee. The medical/surgical history will collect all active conditions and any condition diagnosed within the prior 10 years that the investigator considers to be clinically important. Details regarding the disease for which the participant has enrolled in this study will be recorded separately and not listed as medical history.

#### **8.1.5 Prior and Concomitant Medications Review**

##### **8.1.5.1 Prior Medications**

The investigator or qualified designee will review prior medication use, including any protocol-specified washout requirement, and record prior medication taken by the participant within 28 days before starting the study. Treatment for the disease for which the participant has enrolled in this study will be recorded separately and not listed as a prior medication.

##### **8.1.5.2 Concomitant Medications**

The investigator or qualified designee will record medication, if any, taken by the participant during the study through the Safety Follow-up Visit. Concomitant medications will be recorded for 30 days after the last dose (or longer if related to an SAE or ECI). Refer to Section 6.5.

#### **8.1.6 Assignment of Screening Number**

All consented participants will be given a unique screening number that will be used to identify the participant for all procedures that occur prior to intervention allocation. Each participant will be assigned only 1 screening number. Screening numbers must not be re-used for different participants.

#### **8.1.7 Assignment of Treatment/Randomization Number**

All eligible participants will receive a treatment/randomization number. The treatment/randomization number identifies the participant for all procedures occurring after treatment allocation/randomization. Once a treatment/randomization number is assigned to a participant, it can never be re-assigned to another participant.

A single participant cannot be assigned more than 1 treatment/randomization number.

### **8.1.8 Study Intervention Administration**

Administration of study medication will be witnessed by the investigator and/or study staff.

Study intervention should begin within 3 days of treatment/randomization number assignment.

#### **8.1.8.1 Timing of Dose Administration**

Pembrolizumab will be administered as a 30-minute IV infusion on Day 1 of each 21-day cycle. Sites should make every effort to target infusion timing to be as close to 30 minutes as possible. However, given the variability of infusion pumps from site to site, a window of -5 minutes and +10 minutes is permitted (ie, infusion time is 30 minutes: -5 min/+10 min).

The first dose of study intervention may be administered up to 3 days after the scheduled Day 1. After C1D1, pembrolizumab may be administered up to 3 days before or after the scheduled Day 1 of each subsequent cycle due to administrative reasons.

Refer to Section 6.1 for details on study intervention administration.

Refer to Section 6.6 for information on allowed dosing interruptions.

Refer to Section 7 for criteria for discontinuation of study intervention.

### **8.1.9 Discontinuation and Withdrawal**

Participants who discontinue study intervention prior to completion of the treatment period should be encouraged to continue to be followed for all remaining study visits as outlined in the SoA and Section 8.12.3.

When a participant withdraws from participation in the study, all applicable activities scheduled for the final study visit should be performed (at the time of withdrawal). Any AEs that are present at the time of withdrawal should be followed in accordance with the safety requirements outlined in Section 8.4.

If discontinuation occurs  $\geq 30$  days after the last dose of study intervention, a Safety Follow-up Visit (Section 8.12.3.1) is not required. In this situation, all procedures required at the 30-day Safety Visit and End of Treatment (EOT) are performed once and entered into the EOT visit only.

#### **8.1.9.1 Withdrawal From Future Biomedical Research**

A participant's consent for Future Biomedical Research may be withdrawn by the participant or the participant's legally acceptable representative (as appropriate). A participant's consent may be withdrawn at any time by contacting the principal investigator for the main study. If medical records for the main study are still available, the investigator will contact the Sponsor using the designated mailbox ([contact]). Subsequently, the participant's consent for future biomedical research will be withdrawn. A

letter will be sent from the Sponsor to the investigator confirming the withdrawal. It is the responsibility of the investigator to inform the participant of completion of withdrawal. Any analyses in progress at the time of request for withdrawal or already performed prior to the request being received by the Sponsor will continue to be used as part of the overall research study data and results. No new analyses would be generated after the request is received.

In the event that the medical records for the main study are no longer available (eg, if the investigator is no longer required by regulatory authorities to retain the main study records) or the specimens have been completely anonymized, there will no longer be a link between the participant's personal information and their specimens. In this situation, the request for specimen withdrawal cannot be processed.

#### **8.1.10 Participant Blinding/Unblinding**

This is an open-label study; there is no blinding for this study.

#### **8.1.11 Calibration of Equipment**

The investigator or qualified designee has the responsibility to ensure that any device or instrument used for a clinical evaluation/test during a clinical study that provides information about inclusion/exclusion criteria and/or safety or efficacy parameters shall be suitably calibrated and/or maintained to ensure that the data obtained is reliable and/or reproducible. Documentation of equipment calibration must be retained as source documentation at the study site.

### **8.2 Efficacy Assessments**

#### **8.2.1 Tumor Imaging and Assessment of Disease**

Throughout this section, the term 'scan' refers to any medical imaging data used to assess tumor burden and may include cross-sectional imaging (such as CT or MRI), medical photography, or other methods as specified in this protocol.

In addition to survival, efficacy will be assessed based on evaluation of scan changes in tumor burden over time, until the participant is discontinued from the study or goes into Survival Follow-up. The process for scan collection and transmission to the iCRO can be found in the Site Imaging Manual (SIM). Tumor scans by CT are strongly preferred. For the abdomen and pelvis, contrast-enhanced MRI may be used when CT with iodinated contrast is contraindicated, or when mandated by local practice. The same scan technique should be used in a participant throughout the study to optimize the reproducibility of the assessment of existing and new tumor burden and improve the accuracy of the response assessment based on scans.

Note: for the purposes of assessing tumor scans, the term “investigator” refers to the local investigator at the site and/or the radiological reviewer at the site or at an offsite facility.

In general, scans should include the chest, abdomen, and pelvis.

Expedited confirmation of measurable disease based on RECIST 1.1 by BICR at Screening will be used to determine participant eligibility. Confirmation by the BICR that the participant's imaging shows at least 1 lesion that is appropriate for selection as a target lesion per RECIST 1.1 is required prior to participant allocation.

All scheduled imaging for all study participants will be submitted to the iCRO. In addition, imaging that is obtained at an unscheduled time point for any reason (including suspicion of progression or other clinical reason) should also be submitted to the iCRO if it shows progression, or if it is used to support a response assessment. All imaging acquired within the protocol-specified window of time around a scheduled imaging visit can be classified as pertaining to that visit. Photographs of cutaneous lesions do not need to be submitted to the iCRO.

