Poststudy Anticancer Therapy						X	X	X	All anticancer therapy will be recorded until time of death or termination of Survival Follow-up. If a clinic visit is not feasible, follow-up information may be obtained via telephone or e-mail.

Study Period	Screening Phase	Intervention Phase (Q3W)			End of Treatment	Post-treatment Follow-up			Notes
		1	2	3 and onwards		Safety Follow-up a	Follow-up b	Survival Follow-up	
Treatment Cycle					Discontinuation				Procedures should occur predose on Day 1 of each cycle unless otherwise noted.  Post-treatment Period: Refer to Section 8.12.3.
Scheduled Timing	-28 to -1				At time of d/c	30 days post last dose		~Q12W (telephone)	
Window (days):		+ 3	± 3	± 3		+ 7	± 7	± 7	
Survival Status		<----->						X	After investigator-determined PD or start of new anticancer treatment. In addition, upon Sponsor request, participants may be contacted for survival status at any time during the course of the study (unless this information is not allowed to be provided due to confidentiality).
Efficacy Procedures									
Tumor Imaging (CT/MRI; Chest, Abdomen, and Pelvis)	X	<-----> c			X d			X	Prior scans performed within the screening period but before signing informed consent may be used if consistent with protocol requirements per SIM. All imaging visits have a scheduling window of ±7 days. Imaging to be performed Q12W or sooner if clinically indicated from the date of C1D1 until Week 54 of study treatment, Q24W or sooner if clinically indicated thereafter, or more frequently if required by local standard of care until disease progression per RECIST 1.1.

Study Period	Screening Phase	Intervention Phase (Q3W)			End of Treatment	Post-treatment Follow-up			Notes
		1	2	3 and onwards		Safety Follow-up a	Follow-up b	Survival Follow-up	
Treatment Cycle					Discontinuation				Procedures should occur predose on Day 1 of each cycle unless otherwise noted.  Post-treatment Period: Refer to Section 8.12.3.
Scheduled Timing	-28 to -1				At time of d/c	30 days post last dose		~Q12W (telephone)	
Window (days):		+ 3	± 3	± 3		+ 7	± 7	± 7	
Safety Procedures									
Height	X	X	X	X	X				Pediatric height to be measured at every visit. Adult height measured at Screening only.
Weight	X	X	X	X	X				To be measured at every visit.
Full Physical Examination	X								Within 7 days prior to C1D1.

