T3 (or Free T3), Free T4, and TSH	X		X	X	X				Within 10 days prior to C1D1. Then within 1 day prior to Day 1 of every other cycle starting from Cycle 2 (eg, Cycle 2, 4, 6, 8, etc.) and at EOT. Free T3 is acceptable where T3 cannot be determined.
Hematology	X		X	X	X	X			Blood for hematology and chemistry panel should be collected within 3 days prior to C1D1 and then within 1 day prior to Day 1 of every cycle. Urine for urinalysis should be collected within 3 days prior to C1D1 and then within 1 day prior to Day 1 of every 4 cycles starting from Cycle 4 (eg, Cycle 4, 8, 12, 16, etc.). Every effort should be made to collect samples at the same time of day.
Chemistry Panel	X		X	X	X	X			
Urinalysis	X			X	X	X			
Laboratory Procedures (CENTRAL laboratory)									
Blood for Future Biomedical Research		X							

AE=adverse event; aPTT=activated partial thromboplastin time; BP=blood pressure; C=Cycle; C1D1=Cycle 1 Day 1; CR=complete response; CT=computed tomography; D=Day; ECG=electrocardiogram; ECI=Event of Clinical Interest; ECOG=Eastern Cooperative Oncology Group; EOT=End of Treatment; HIV=human immunodeficiency virus; INR=international normalized ratio; MRI=magnetic resonance imaging; PD=progressive disease; PT=prothrombin time; Q3W=every 3 weeks; Q12W=every 12 weeks; Q24W=every 24 weeks; RECIST=Response Evaluation Criteria In Solid Tumors; SAE=serious adverse event; SIM=Site Imaging Manual; T3=triiodothyronine; T4=thyroxine; TSH=thyroid stimulating hormone; WOCBP=women of childbearing potential.

- a If the EOT visit occurs  $\geq 30$  days after the last dose of study intervention, a Safety Follow-up Visit is not required. In this situation, all procedures required at the 30-day Safety Visit and EOT are performed once and entered into the EOT visit only.
- b In the Follow-up Phase, participants should be assessed Q12W until Week 54 after C1D1 ( $\pm 7$  days); Q24W thereafter or sooner if clinically indicated, or more frequently if required by local standard of care, until disease progression per RECIST 1.1, to monitor disease status.
- c The same imaging technique regarding modality and the use of contrast should be used in a participant throughout the study to optimize the visualization of existing and new tumor burden. Imaging of any anatomy that shows disease either at Screening or in subsequent evaluations will be required and should be submitted to the imaging contract research organization (iCRO).

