### **4.2.1 Rationale for Endpoints**

#### **4.2.1.1 Efficacy Endpoints**

This study will use ORR, defined as the proportion of participants who have best response as CR or PR. Responses are based on RECIST 1.1 criteria as assessed by blinded independent central review (BICR) as the primary endpoint. Objective response rate (ORR) is an acceptable measure of clinical benefit for a late stage study that demonstrates superiority of a new antineoplastic therapy, especially if the magnitude of the effect is large and the therapy has an acceptable risk/benefit profile. The use of BICR and RECIST 1.1 to assess ORR is

typically considered acceptable by regulatory authorities. Images will be submitted to an imaging CRO (iCRO) and read by independent central review blinded to treatment assignment to minimize bias in the response assessments.

Secondary efficacy endpoints include DOR, PFS, and OS.

Duration of response (DOR) as assessed by BICR per RECIST 1.1 criteria is a commonly accepted endpoint by both regulatory authorities and the oncology community to assess durability of responses to oncology treatments.

In this study, PFS is to be assessed by BICR per RECIST 1.1 criteria. The use of BICR and RECIST 1.1 to assess PFS is typically considered acceptable by regulatory authorities. Images will be submitted to an iCRO and read by independent central review blinded to treatment assignment to minimize bias in the response assessments. In addition, the final determination of radiologic progression will be based on the central assessment of progression, rather than a local site investigator/radiology assessment.

Overall survival (OS) is the gold standard for a “hard endpoint” in clinical studies in the area of oncology.

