#### **8.2.1.5 iRECIST Assessment of Disease**

iRECIST is based on RECIST 1.1, but adapted to account for the unique tumor response seen with immunotherapeutic drugs. iRECIST will be used by the investigator to assess tumor response and progression, and make treatment decisions. When clinically stable, participants should not be discontinued until progression is confirmed by the investigator, working with local radiology, according to the rules outlined in Appendix 8. This allowance to continue treatment despite initial radiologic PD takes into account the observation that some participants can have a transient tumor flare in the first few months after the start of immunotherapy, and then experience subsequent disease response. This data will be captured in the clinical database.

Clinical stability is defined as the following:

- Absence of symptoms and signs indicating clinically significant progression of disease
- No decline in ECOG performance status (or Lansky scale, if appropriate)
- No requirements for intensified management, including increased analgesia, radiation, or other palliative care

Any participant deemed clinically unstable should be discontinued from study intervention at site-assessed first radiologic evidence of PD, and is not required to have repeat tumor imaging for confirmation of PD by iRECIST.

If the investigator decides to continue treatment, the participant may continue to receive study intervention and the tumor assessment should be repeated 4 to 8 weeks later to confirm PD by iRECIST, per investigator assessment. Images should continue to be sent in to the iCRO for potential retrospective BICR.

If repeat imaging does not confirm PD per iRECIST, as assessed by the investigator, and the participant continues to be clinically stable, study intervention may continue and follow the regular imaging schedule. If PD is confirmed, participants will be discontinued from study intervention.

If a participant has confirmed radiographic progression (iCPD) as defined in Appendix 8, study intervention should be discontinued; however, if the participant is achieving a clinically meaningful benefit, an exception to continue study intervention may be considered following consultation with the Sponsor. In this case, if study intervention is continued, tumor imaging should continue to be performed following the intervals as outlined in Section 8 and submitted to the iCRO.

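### Section 8.2.1 requires an unscheduled scan to go to central review only if it shows progression or supports a response, so a local non-progression read can delay or lose a BICR progression

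*Combined protocol and SAP*

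**What the plan says.** Section 8.2.1 sets two rules. For scheduled scans: "All scheduled imaging for all study participants will be submitted to the iCRO". For an unscheduled scan, whatever prompted it (suspected progression included), the image "should also be submitted to the iCRO if it shows progression, or if it is used to support a response assessment". The sentence does not say who judges whether the scan shows progression.

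Other text bears on the same images:

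- Section 8.2.1 adds: "All imaging acquired within the protocol-specified window of time around a scheduled imaging visit can be classified as pertaining to that visit". The SoA (Section 1.3) sets that window: "All imaging visits have a scheduling window of ±7 days".
- SoA footnote c covers imaging of anatomy that "shows disease either at Screening or in subsequent evaluations will be required and should be submitted to the imaging contract research organization", with no condition on the local read.
- Section 8.2.1.5, on imaging after first local progression when treatment continues: "Images should continue to be sent in to the iCRO for potential retrospective BICR".
- Section 4.2.1.1 says images are "read by independent central review blinded to treatment assignment to minimize bias in the response assessments", and gives the central assessment, not the site's, the final word on radiologic progression.
- Section 8.2.1 also states: "The process for scan collection and transmission to the iCRO can be found in the Site Imaging Manual". That manual is not among the documents.

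Section 9.6.1.3 dates PFS progression by BICR. Tables 8 and 9 censor DOR and PFS at the last assessment before new anticancer therapy.

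**The concern.** When the submission test is applied, BICR has not seen the scan. Someone at the site therefore decides whether it shows progression, knowing the treatment. The scan on which site and central reader could disagree, with the site seeing no progression and BICR seeing it, is the one this sentence does not require to be sent.

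Unscheduled scans are foreseen: the schedule allows imaging sooner if clinically indicated or if local practice requires it. They matter most after Week 54, when routine scans are 24 weeks apart.

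The trial has one arm, so no control group shares the error. Section 4.2 rests the postmarketing case on response rate and on durable responses by BICR, and Table 10 lists DOR under the key secondary heading. A filter that lengthens BICR DOR and PFS acts on that case.

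**Working it through.** **The plan's own figure.** The plan gives no figure on this point. Its precision figure reproduces: 28/50 = 56%, exact 95% CI 41.3% to 70.0%, half-width about 14.4 points. Nothing below changes it.

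**Which scans are exposed.** A scan is not required under Section 8.2.1 if it is unscheduled, outside every ±7-day window, read locally as non-progression and not used for response. Scans inside a window can count as the scheduled visit. Scans read locally as progression are sent, and so are the repeat scans that follow.

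**Direction.** Appendix 8 gives the target-lesion threshold: an increase of at least 20% and at least 5 mm from nadir. Removing a scan takes away one possible progression date and leaves the nadir equal or higher. With fixed measurements, progression therefore cannot come earlier. In 60,000 random eight-point lesion series with about 30% of follow-up scans dropped, progression was earlier in 0, later in 13,535 and absent in 5,658. Only the zero carries over to the trial; the other counts depend on the simulated series.

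**Longest delay.** The site saw no progression, so scheduled imaging continues (Section 8.2.1.2) and the next scheduled scan is sent.

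- To Week 54: interval 84 days, next scan at latest day 91. An off-window scan falls on day 8 or later after the previous nominal visit, so the delay is at most 91 − 8 = 83 days, about 12 weeks.
- After Week 54: 168 + 7 − 8 = 167 days, about 24 weeks.
- Section 8.2.1.2 lets a participant skip a scheduled scan that falls fewer than 4 weeks after a confirmation scan, which could lengthen the gap.
- Death before the next scan counts as an event, subject to Tables 8 and 9. If new therapy starts first, the progression is lost and the participant is censored.

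**Possible size.** The documents give neither the rate of unscheduled scans nor the local/central discordance rate. Assumptions:

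- u = 30% or 60% of progressors have an unscheduled scan, uniformly timed between true progression and the next scheduled scan.
- d = 10%, 20% or 40% of those scans are read as non-progression locally and progression by BICR.
- Scans within one week before the next visit count as that visit.
- Scheduled scans fall at Weeks 12, 24, 36, 48, 72, 96 and so on.
- Every event is a progression, with no deaths, new therapy or censoring.

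True PFS was either exponential with median 16.8 months, or piecewise exponential through 52% at 12 and 48% at 24 months (both from the earlier study, Section 2.2.1.3). Medians in months are shown as all scans sent → current rule:

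| u | d | Delayed, exp. / piecewise | Median, exp. | Median, piecewise |
|---|---|---|---|---|
| 30% | 10% | 2.4% / 2.2% | 19.03 → 19.16 | 22.08 → 22.08 |
| 30% | 20% | 4.7% / 4.4% | 19.03 → 19.32 | 22.08 → 22.08 |
| 30% | 40% | 9.5% / 8.8% | 19.03 → 19.69 | 22.08 → 22.08 |
| 60% | 10% | 4.7% / 4.4% | 18.38 → 18.48 | 20.83 → 21.03 |
| 60% | 20% | 9.6% / 8.8% | 18.38 → 18.58 | 20.83 → 21.22 |
| 60% | 40% | 19.1% / 17.6% | 18.38 → 18.89 | 20.83 → 21.68 |

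As a rough check, u × d runs from 0.30 × 0.10 = 3% to 0.60 × 0.40 = 24%; removing scans that fall in the next window brings this to about 2% to 19%. The largest shift in the median is 21.68 − 20.83 = 0.85, about 0.9 months. The zero shifts arise where both medians land on the Week 96 scan. Mean delay among those delayed is 5.9 to 6.3 weeks. PFS at 12 months moves by at most 0.07 points, partly because that landmark falls soon after the Week 48 scan.

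**Head count.** If 24-month PFS were 48%, there would be 50 × 0.52 = 26 events by then, deaths included. Applying 2% to 19% gives about 0.5 to 5 participants.

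**The case against.** The strongest reply is that Section 8.2.1 states when an unscheduled scan should be sent and does not bar sending others. Footnote c, read literally, already asks for images of known disease sites, and every participant has BICR-confirmed measurable disease before allocation. Post-progression and in-window scans are largely covered, and the Site Imaging Manual may close the gap. This stands as a limit on the claim: a reader might infer that sites withhold scans, but the documents do not show that. What remains is that footnote c and Section 8.2.1 give sites different instructions.

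The rule also helps compared with reading scheduled scans only. At u = 30%, d = 20% and the exponential curve, median PFS is 22.1 months on scheduled scans alone, 19.3 under the current rule and 19.0 with all scans. It thus recovers 2.8 of 3.1 months. That stands for those assumptions, but the remaining error is still one-sided.

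Three stronger readings are tempting and not supported:

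- *The filter only lengthens observed time.* An unsent non-progression scan can also move a censoring date earlier, because censoring is at the last assessment.
- *The purpose of BICR is defeated.* BICR still reads all scheduled scans and receives every scan that the site reads as progression.
- *The primary ORR is inflated.* Scans showing progression and scans supporting response are both sent, and in the earlier study 26 of 28 responses occurred by the first on-study scan at about 3 months. A repeat scan that fails to confirm a response might arguably escape the wording, but that depends on how broadly support for a response assessment is read. No size can be given.

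**Conclusion.** The point holds as a gap in the submission rule and an inconsistency between sections. Under Section 8.2.1, an off-window scan read locally as non-progression and not used for response need not reach BICR. That sits badly with Section 4.2.1.1 and with footnote c. Against full submission, a BICR progression date is unchanged, delayed or lost, never earlier, which favours longer PFS and DOR.

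The two bounds on the delay hold per affected participant and assume that no scheduled scan is skipped. The estimated effect is modest and rests wholly on the assumed scan and discordance rates; it leaves out progressions lost to new therapy and any earlier censoring. Applying an assumed rate to all 50 participants would overstate it, since only progressors can have a delayed progression. PFS and DOR are secondary endpoints and the study tests no hypothesis. The case for change is that the error runs in one direction for progression dates and is cheap to remove.

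**What to change.** Amend Section 8.2.1 so that all on-study tumor imaging used to assess disease (CT, MRI and bone scans), scheduled or unscheduled, is submitted to the iCRO and read by BICR whatever the local result. Photographs of cutaneous lesions stay exempt, as now. Bring SoA footnote c and Section 4.2.1.1 into line with that sentence. In the study report, state how many unscheduled scans were obtained and how many BICR read.

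The cost is some extra image transfers and reads by the existing vendor, and some time points with only part of the anatomy imaged, which BICR may find not evaluable. Participants have no extra scans, and the sample size and the ORR interval method do not change.
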